#### 14.3.17 Description of the Bayesian analyses and design characteristics

The design characteristics is based on 92 randomised subjects (69 in the delgocitinib cream 20 mg/g group and 23 in the cream vehicle group).

For each endpoint, the choice of the between-trial heterogeneity parameter ( $\tau$ ) and the weight on the non-informative part of the prior is described. In addition, the degree of borrowing is described by the ESS and finally, the influence of the type I error and power investigated.

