Secondary objectives: To evaluate the health-related quality of life of twice-daily applications of delgocitinib cream 20 mg/g compared with cream vehicle in the treatment of adolescents with moderate to severe CHE.	Bayesian and Frequentist.	Primary.	Response achieved without IEs.	Initiation of rescue treatment, permanent discontinuation of IMP. Composite strategy.	Risk difference.	Key secondary endpoints: 
 
• Reduction of HESD itch score (weekly average) of <math>\geq 4</math> points from baseline at Week 16.
 
• Reduction of HESD pain score (weekly average) of <math>\geq 4</math> points from baseline at Week 16.
 
• Reduction of HESD score (weekly average) of <math>\geq 4</math> points from baseline at Week 16.
 

	Frequentist.	Primary.	Change from baseline to Week 16 without IEs.	Initiation of rescue treatment, permanent discontinuation of IMP. Composite strategy.	Difference in mean change.	Secondary endpoint: 
 
• Change in cDLQI score from baseline to Week 16.
 

1) Among subjects with a baseline HESD itch score (weekly average)  $\geq 4$  points.

2) Among subjects with a baseline HESD pain score (weekly average)  $\geq 4$  points.

3) Among subjects with a baseline HESD score (weekly average)  $\geq 4$  points.

**Abbreviations:** cDLQI = Children's Dermatology Life Quality Index; CHE = chronic hand eczema; HECSI = Hand Eczema Severity Index; HECSI-90 = at least 90% improvement in HECSI score from baseline; HESD = Hand Eczema Symptom Diary®; IE = intercurrent event; IGA-CHE = Investigator's Global Assessment for chronic hand eczema®; IGA-CHE TS = IGA-CHE treatment success, i.e. an IGA-CHE score of 0 (clear) or 1 (almost clear) with a  $\geq 2$ -step improvement from baseline; TS = treatment success.

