**Panel 5: Trial analysis sets**

Trial analysis set	Description
FAS	

All randomised to treatment and exposed subjects. Subjects will be included in the analyses according to the planned treatment.

SAF	

All subjects who are exposed to IMP. Subjects will be included in the analyses according to the treatment they actually received.

**Abbreviations:** FAS = full analysis set, IMP = investigational medicinal product, SAF = safety analysis set.

The FAS is used to analyse endpoints related to the efficacy objectives, and the SAF is used to analyse the endpoints and assessments related to safety.

For analyses of safety all subjects who have had at least one application with delgocitinib 20 mg/g will be analysed in the delgocitinib 20 mg/g treatment group. This is done to ensure that no drug reactions to delgocitinib 20 mg/g treatment will erroneously be assigned to the vehicle treatment group.

THIS DOCUMENT CONTAINS CONFIDENTIAL INFORMATION AND MUST NOT BE COPIED OR MADE AVAILABLE TO ANY THIRD PARTY WITHOUT THE PRIOR WRITTEN CONSENT OF THE LEO PHARMA GROUP

Exclusions from the FAS can be considered in special cases as described in ICH E9, Section 5.2.1., Full Analysis Set. If it is decided to exclude a randomized subject from the FAS, a justification addressing ICH E9 will be given in the Classification Brief before breaking the randomization code.

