## **5 Statistical analysis**

### **5.1 General principles**

All frequentist significance tests will be one-sided using the 2.5% significance level. Operationally, the one-sided (superiority) hypotheses will be evaluated by deriving the two-sided p value; the null hypothesis will be rejected if the p value is smaller than 5% and if the point estimate is in favor of the alternative hypothesis.

All confidence intervals will be presented with 95% degree of confidence, unless otherwise specified.

An observed-cases approach will be used for tabulations of data by visit (that is, involving only those subjects who attended each specific visit).

Categorical data will be summarised using the number and percentage of subjects in each category and treatment group. Continuous data will be summarised using the mean, median, SD, 1st quartile, 3rd quartile, minimum, and maximum values.

Baseline measurements will be defined as the latest available observation at or prior to the date of randomization. Subjects without a baseline measurement for a given efficacy score will be excluded from the corresponding analysis.

In case of randomization in wrong stratum with respect to baseline IGA-CHE score, the statistical analyses will use the baseline IGA-CHE score confirmed by the investigator in the eCRF. This is due to the fact that the disease severity according to baseline IGA-CHE score is considered to be a strong prognostic factor for the treatment effect.

Simulation seed used for MI will be 1331426 for both types of imputation (MI based on MAR and MI based on Bernoulli distribution).

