#### **5.5.1.7 Primary endpoint analysis using the primary estimand, Bayesian approach**

For the Bayesian analysis of the primary endpoint the estimand used is the primary estimand i.e., the composite strategy. The treatment effect (defined as proportion of responders for delgocitinib cream 20 mg/g minus the proportion of responders for cream vehicle) will be evaluated based on the calculated posterior distribution of the treatment difference.

Delgocitinib cream 20 mg/g is considered superior to cream vehicle if the 2.5% percentile of the posterior distribution of the treatment difference is  $\geq 0$ . Appendix [7.2.2](#) provides an example of R code to perform the Bayesian analyses.

The MAP approach using a hierarchical model for the between-study heterogeneity is used to derive the informative priors from historical data. The prior for the between-trial heterogeneity for the primary endpoint IGA-CHE TS, which controls the amount of borrowing from historical information, is set to  $\tau = 0.5$  and the prior weight on the non-informative part of the prior is set to 0.2 (20%).

The 'gMAP' function in the statistical package 'RBesT' in R is used for the calculations. The seed used for both vehicle and delgocitinib cream 20 mg/g is 1331426, the number of iterations is set to 50.000 and the warmup is set to 5000.

For IGA-CHE the historical response rates from LP0133-1401 and LP0133-1402 (see [Panel 9](#)) are used to calculate the informative MAP prior both for the cream vehicle as well as for the delgocitinib cream 20 mg/g.

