#### 5.5.1.8 Binary key secondary endpoints analyses using the primary estimand, Bayesian approach

The Bayesian analyses of the primary estimand for the key secondary endpoints will be performed in a similar manner as for the primary endpoint IGA-CHE. The various number of responders and beta mix components for vehicle and delgocitinib 20 mg/g can be found in the following subsections.

The prior for the between-trial heterogeneity  $\tau$  is set to 0.5 and the prior for the weight on the non-informative part of the prior is set to 0.2 for all key secondary endpoints.

As for the Bayesian approach of the primary endpoint analysis using the primary estimand the prior distributions for the key secondary endpoints shown in the SAP are fixed and will not change after un-blinding.

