### 7.2.2 R code for Bayesian analyses

Calculation of Beta-mix components for prior distribution done before DBL and unblinding of data:

```
seed.Veh<-1331426
seed.del<-1331426
weight.value <- 0.2
tau.priorvalue <- 0.5

map_mcmc_veh <- gMAP(cbind(r, n-r) ~ 1 | study, data=xxx,
tau.dist="HalfNormal",
                    tau.prior=tau.priorvalue, beta.prior=100,
family=binomial, iter=50000, warmup=5000,
                    thin=5, init = 1, chains=6,cores=1L)
```

Conversion of the MAP prior to a parametric representation with the automixfit function:

```
map <- automixfit(map_mcmc_veh, k=10)
```

Robustification of parametric representation of the prior:

```
map_robust <- robustify(map, weight=weight.value,
mean=1/2,tau.prior=tau.priorvalue)
```

The parameter settings and number of iterations mentioned above will not be changed after DBL. The code mentioned below will be run on unblinded data. Here, the number of iterations may be increased if results are not clearly interpretable.

Calculation of the posterior distribution

```
post <- postmix(prior, r = number of responders, n = number of randomised)
```

Calculation of probability that the difference is smaller than 0

```
prob_smaller_iga <- pmixdiff(post_trt1, post_trt2, 0, lower.tail=FALSE)
prob_smaller_iga > 0.975
```

Sampling of 1.000.000 differences between posteriors

```
rM_iga <- rmixdiff(post_trt1, post_trt2, n=1E6)
rM_mean_iga<- mean(rM_iga)
```

THIS DOCUMENT CONTAINS CONFIDENTIAL INFORMATION AND MUST NOT BE COPIED OR MADE AVAILABLE TO ANY THIRD PARTY WITHOUT THE PRIOR WRITTEN CONSENT OF THE LEO PHARMA GROUP

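### The SAP's only posterior code sets n to the number randomised, which contradicts the baseline restriction of the three HESD key secondary endpoints; the HESD design figures also assume that all 69/23 qualify

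*SAP*

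**What the plan says.** - **Posterior code.** SAP 7.2.2 has a single posterior line, "post <- postmix(prior, r = number of responders, n = number of randomised"). The text just above it says the code that follows is what will be applied to the unblinded data; the only latitude given is more iterations.
- **Status of the code.** SAP 5.5.1.7, on the primary endpoint, says the appendix "provides an example of R code to perform the Bayesian analyses". The result objects in the appendix have IGA names.
- **Key secondary endpoints.** SAP 5.5.1.8 says their Bayesian analyses "will be performed in a similar manner as for the primary endpoint IGA-CHE". It gives responder counts and prior components for each endpoint, but no denominator for the adolescent data.
- **HESD populations.** The footnotes to SAP Panel 1 restrict each HESD endpoint, for example "Among subjects with a baseline HESD itch score (weekly average") at or above 4 points, and likewise "Among subjects with a baseline HESD pain score (weekly average") and the total score.
- **Analysis set.** SAP Panel 5 defines the full analysis set (FAS) as "All randomised to treatment and exposed subjects". SAP 5.1 adds: "Subjects without a baseline measurement for a given efficacy score will be excluded from the corresponding analysis".
- **Design figures.** Protocol 14.3.17 opens with "The design characteristics is based on 92 randomised subjects", split 69 and 23. Sections 14.3.17.3.2 to 14.3.17.3.4 then report power above 80% and type I error below 5% for HESD total, itch and pain, with no allowance for the restriction.

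**The concern.** Three of the five endpoints in the confirmatory hierarchy are defined in a subset, and the only written denominator for their posterior is everyone randomised. The two cannot both be followed. A subject with a baseline below 4 cannot fall by 4 points, so counting that subject in n adds a certain non-responder. The diluted rate is then combined with a prior built from subjects who could respond, so the agreement between prior and data is judged on the wrong scale. In a fixed sequence, a wrong call on one HESD endpoint also decides whether later endpoints are tested at all. If the contradiction is settled only after unblinding, choosing n becomes a discretionary step in the confirmatory analysis.

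The design figures have a related gap: if fewer than 92 subjects qualify, HESD power and type I error are not those of 69/23.

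**Working it through.** **Inputs.** Rounded prior components from SAP Panels 16–17 (itch), 19–20 (pain) and 22–23 (total), weights rescaled to sum to 1. Adult average rates, vehicle and delgocitinib, from Protocol Panels 42, 45 and 39: itch 21.1% and 47.4%, pain 24.3% and 49.6%, total 21.6% and 45.5%. Success means a posterior probability above 0.975 that the difference exceeds zero.

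**Formulas.** With r responders among n, component k becomes Beta(a_k + r, b_k + n − r), with weight proportional to w_k · B(a_k + r, b_k + n − r) / B(a_k, b_k). Power is the sum, over all pairs of responder counts, of the two binomial probabilities for pairs that meet the success rule. Type I error is the same sum with both arms at the adult vehicle rate. The enumeration is exact and uses numerical integration for the probability.

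**Step 1: the plan's own figures.** At 69/23, power for itch/pain/total is 92.8/88.6/87.1% and type I error 2.5/3.5/3.1%. This agrees with the stated >80% and <5%.

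**Step 2: qualifying shares in the adult trials.** HESD denominators divided by the HECSI-90 denominators of the same arm (Protocol Panels 36, 39, 42, 45), delgocitinib then vehicle:

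| Trial | Itch | Pain | Total |
|---|---|---|---|
| 1401 | 323/325, 161/162 (99.4, 99.4%) | 291/325, 149/162 (89.5, 92.0%) | 309/325, 156/162 (95.1, 96.3%) |
| 1402 | 309/313, 156/159 (98.7, 98.1%) | 294/313, 141/159 (93.9, 88.7%) | 308/313, 153/159 (98.4, 96.2%) |
| 1273 | 26/41, 24/38 (63.4, 63.2%) | 20/41, 15/38 (48.8, 39.5%) | 27/41, 24/38 (65.9, 63.2%) |

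The documents do not say whether the small phase 2b numbers come only from the baseline restriction. They give no adolescent share, so a range is assumed below.

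**Step 3: eligible n used throughout, and the code line taken literally.** In the literal case the responders arise among the eligible subjects but n is entered as 69/23. Each cell is itch/pain/total, in percent.

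| Eligible (share) | Power, eligible n | Type I error, eligible n | Power, n = 69/23 |
|---|---|---|---|
| 66/22 (96%) | 91.6/88.0/87.1 | 3.1/3.6/3.6 | 92.8/88.3/87.0 |
| 62/21 (90%) | 91.7/85.9/85.0 | 3.4/3.8/3.9 | 91.4/85.9/84.7 |
| 52/17 (75%) | 86.8/83.1/80.4 | 3.7/4.6/4.3 | 80.6/73.0/71.3 |
| 45/15 (65%) | 86.1/80.0/77.0 | 4.2/5.4/5.5 | 57.2/49.8/47.9 |

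If eligibility is instead random for each subject (response rates multiplied by 0.65, n = 69/23), the last cell becomes 55/49/47%.

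**Step 4: single outcomes.** The wrong n can move a result in either direction.

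- Pain, 22/45 against 4/15: probability 0.993, mean difference 25.1 points, success. Entered as 22/69 against 4/23: 0.964, 14.7 points, failure.
- Total, 24/45 against 5/15: probability 0.974, failure. Entered as 24/69 against 5/23: 0.987, success. The vehicle rate of 5/15 = 33.3% conflicts with the adult 21.6%, but 5/23 = 21.7% matches it, so the wrong n hides the conflict.

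**The case against.** The strongest reply is that nothing in the SAP orders HESD responders to be divided by all randomised subjects. The code is labelled an example, its result objects are named for IGA, its inputs are placeholders, and SAP Panel 9 is the only historical panel whose denominator is labelled as randomised. The restriction to baseline at or above 4 is repeated in the endpoint definitions of both documents, including the footnote to the Bayesian column of SAP Panel 8. The HESD priors already use the subset, and SAP 5.1 removes subjects without a baseline. A careful programmer would use the subset. The first application is on site on the day of randomisation, so randomised and FAS should nearly coincide, and a baseline IGA-CHE score is needed for entry.

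Most of this stands, and it limits the point. A reader might infer that the plan divides by the number randomised for every endpoint. That is only an inference from one generic line, and the endpoint definitions point the other way. A reader might also infer that the stated HESD power holds only if nearly everyone qualifies. It does not: all six bounds still hold at 52/17. Nor is power near 50% an expected result; it needs both the literal reading and a qualifying share far below phase 3.

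The reply does not remove the contradiction. SAP 1 promises enough detail to reproduce every analysis, and for HESD the only denominator written into the posterior step is the wrong one.

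**Conclusion.** The point holds at moderate severity. The SAP's one posterior line conflicts with the defined HESD populations and with the denominators behind their priors. It also names a set that is not the FAS, though that matters little in practice. Followed literally, it can turn a success into a failure or the reverse. The expected loss is negligible if about 90% or more qualify, 6 to 10 points of power at 75%, and roughly 29 to 30 points at 65%.

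The design figures are a secondary matter. With the correct n, the stated bounds hold at phase 3 shares and at 75%. At 65%, itch still meets both, pain only reaches 80.0% power, total falls to 77.0%, and type I error passes 5% for pain and total. The 65% share is an assumption close to the phase 2b numbers for itch and total. Phase 3, which enrolled the same severity range, gives about 89–99%.

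These results rest on adult response rates, priors rounded to two decimals, and an eligible split close to 3:1. The plotted design curves (Protocol Panels 40, 43, 46) are not visible, so only the stated inequalities could be checked. The primary endpoint is essentially unaffected.

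**What to change.** Before unblinding, replace the denominator in SAP 7.2.2 with a definition per endpoint, and repeat it in SAP 5.5.1.7 and 5.5.1.8:

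- HESD itch, pain and total: FAS subjects in the arm whose baseline weekly average for that score is at least 4.
- IGA-CHE TS and HECSI-90: FAS subjects in the arm with a baseline value for that score.

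Then restate HESD power and type I error for the eligible numbers. The SAP was written after blind review, so the total eligible per endpoint can be counted without unblinding and split 3:1 for the calculation; a short range around that split would cover imbalance.

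The cost is one line of code, a sentence in each of two sections, three recalculated sets of design figures, and possibly a slightly lower stated HESD power. No prior, threshold or endpoint changes.

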## **7.3 Appendix 3: Subject disposition and other baseline characteristics**

### **7.3.1 Demographics and other baseline characteristics**

Demographics and other baseline characteristics will be summarized as described in the CTP Section 14.3.2.

### **7.3.2 Subject disposition**

Subject disposition is summarized as described in the CTP Section 14.3.1.

In addition, time to permanent discontinuation of IMP will be presented for subjects in FAS by treatment group using Kaplan-Meier plots. Subjects completing the treatment period will be censored at the day of the Week 16 visit (administrative censoring).

### **7.3.3 Medical history**

Medical history will be coded using MedDRA.

Medical history will be split between past and current medical history. Past medical history is medical history confirmed not to be ongoing at screening. Current medical history is medical history confirmed to be ongoing at screening.

Past and current medical history will be tabulated by SOC and PT per treatment group and for all randomized subjects.

CHE treatment history will be tabulated by treatment group for all randomized subjects.

All CHE treatment history will be listed.

### **7.3.4 Concomitant medication**

Concomitant medication will be coded up to ATC level 4 using the WHODrug.

Concomitant medication will be split between prior medication and concomitant medication. Prior medication is medication with a stop date prior to first IMP application, concomitant medication is a medication that is ongoing at the date of first IMP application, or with a start date on or after the date of first IMP application.

ATC level 1-4 will be presented for prior medication and concomitant medication by treatment group for all randomized subjects.

THIS DOCUMENT CONTAINS CONFIDENTIAL INFORMATION AND MUST NOT BE COPIED OR MADE AVAILABLE TO ANY THIRD PARTY WITHOUT THE PRIOR WRITTEN CONSENT OF THE LEO PHARMA GROUP

### 7.3.5 Rescue treatment

Rescue treatment is defined as treatment (medication or procedure) initiated to treat intolerable CHE symptoms during the treatment and follow-up periods, see CTP Section 9.5. Rescue medication will be coded up to ATC level 4 using WHODrug. Rescue procedures will be coded using MedDRA.

Rescue treatment initiated on or after the date of first IMP application (most often the baseline visit) and until Week 16 will be tabulated by treatment for the FAS. All rescue treatment will be listed.

Time to initiation of rescue treatment will be presented for subjects in the FAS by treatment group. Subjects completing the treatment period without initiating rescue treatment will be censored at day of the Week 16 visit. Subjects who permanently discontinue IMP without initiation of rescue treatment will be censored at the day of their last visit. Kaplan-Meier curves of time to initiation of rescue treatment will be estimated by treatment group.

### 7.3.6 Treatment compliance and drug accountability

Treatment compliance will be presented for the safety analysis set by treatment group. Analysis of treatment compliance will be based on assessments from the eDiary.

Treatment compliance will be presented as the percentage of days where the subjects did not apply IMP as instructed or did not fill in the eDiary out of the expected number of days for specific periods of time (Day 1-7, Day 8-14, Day 15-28, Day 29-56, Day 57-84, Day 85-112 days, total treatment period).

Drug accountability is based on the weight of the returned tubes, and only returned tubes are considered. The total amount of IMP used and the average weekly amount of IMP used during the trial will be presented for the safety analysis set. Calculation of total amount of IMP and the average weekly amount of IMP used is described in the ADRG.

### 7.3.7 Protocol deviations

Important subject level protocol deviations will be summarized by country and site for all screened subjects.

Important trial level, country level, site level and subject level protocol deviations will be listed for all screened subjects.

THIS DOCUMENT CONTAINS CONFIDENTIAL INFORMATION AND MUST NOT BE COPIED OR MADE AVAILABLE TO ANY THIRD PARTY WITHOUT THE PRIOR WRITTEN CONSENT OF THE LEO PHARMA GROUP

